## 1. VERSION HISTORY

**Table 1. Summary of Changes**

Version/ Date	Associated Protocol Amendment	Rationale	Specific Changes
1 15 Aug 2023	Original 19 Jun 2023	N/A	N/A
2 25 Mar 2024	Protocol Amendment 1 07 Nov 2023	To remove analysis related to PK collection via Tasso to be consistent with Protocol Amendment 1, and modify safety analysis for ECG and VS.	
Section 2.2 removed tertiary objective and endpoints related to Tasso micro-sampling device
 
Section 3.1, 3.2 updated notation for <math>K_{el}</math>
 
Section 3.3 removed analysis of the endpoints related to Tasso micro-sampling device
 
Section 3.4 modified baseline definitions for ECG and VS
 
Section 3.5.3 modified language on post-baseline for calculation of change from baseline in vital signs; removed calculation for maximum decrease/increase
 
Section 3.5.4 modified language on post-baseline for calculation of change from baseline in ECG; removed calculation for maximum decrease/increase
 
Section 4, removed section reference related to PK analysis of Tasso micro-sampling device
 
Section 6.4 removed PK concentration presentation for Tasso micro-sampling device
 
Section 6.5 modified language for demographic summary to be by gender and overall
 
Section 6.6.3 modified language for vital signs summary to be for Periods 1-3 and Period 4

**Table 1. Summary of Changes**

Version/ Date	Associated Protocol Amendment	Rationale	Specific Changes
			
Section 6.6.4 modified language for ECG summary to be for Periods 1-3 and Period 4; removed using average for replicate measurements
 
Appendix 1, updated categorization of ECG and VS to be based on change from baseline

## 2. INTRODUCTION

This statistical analysis plan (SAP) provides the detailed methodology for summary and statistical analyses of the data collected in Study B7981086. This document may modify the plans outlined in the protocol; however, any major modifications of the primary endpoint definition will also be reflected in a protocol amendment.

(copied from protocol)

Ritlecitinib is a covalent and irreversible inhibitor of JAK3 with high selectivity over the other JAK isoforms (JAK1, JAK2, and TYK2). Ritlecitinib also inhibits irreversibly the tyrosine kinase expressed in TEC family kinases with selectivity over the broader human kinome. Treatment with ritlecitinib is expected to inhibit the inflammatory pathways mediated by IL-7, IL-15 and IL-21, all implicated in UC, CD, AA, RA, and vitiligo. Moreover, due to lack of activity against the other JAK isoforms, ritlecitinib is expected to spare immunoregulatory cytokines such as IL-10, IL-27 and IL-35, which are critical to the maintenance of immunosuppressive functions and immune homeostasis.

The purpose of the study is to evaluate the PK, safety, and tolerability of ritlecitinib following single oral doses as solution and MR formulations in healthy, adult participants under fasted and fed conditions. The objective is to evaluate the relative bioavailability and food effect of 2 new MR capsule formulations, MR1 and MR2. Overall, results from this study will facilitate further development of an MR formulation for future clinical studies.

### 2.1. Modifications to the Analysis Plan Described in the Protocol

Not applicable.

### 2.2. Study Objectives, Endpoints, and Estimands

As this is an inpatient, healthy volunteer study, estimands are not applicable. The table below is copied directly from the protocol.

Objectives	Endpoints
Primary:	Primary:

 
To determine the PK profile and relative bioavailability of ritlecitinib as 2 MR capsule formulations, MR1 and MR2, relative to solution formulation under fasted conditions in healthy adult participants.
 
	
 
PK parameters of ritlecitinib (fasted): <math>C_{max}</math>, <math>AUC_{inf}</math> (if data permit), otherwise <math>AUC_{last}</math>
 

Secondary:	Secondary:

 
To evaluate the effect of food on ritlecitinib exposure following administration as 2 MR capsule formulations, MR1 and MR2 in healthy adult participants.
 
	
 
PK parameters of ritlecitinib (fed): <math>C_{max}</math>, <math>AUC_{inf}</math> (if data permit), otherwise <math>AUC_{last}</math>.
 

 
To evaluate safety and tolerability of ritlecitinib following single oral administration as MR1 and MR2 capsule formulations in healthy adult participants.
 
	
 
Assessment of AEs, clinical laboratory tests, vital signs and 12-lead ECG.
 

Tertiary/Exploratory:	Tertiary/Exploratory:

 
To estimate additional PK parameters of ritlecitinib following single oral administration as MR1 and MR2 capsule formulations in healthy adult participants.
 
	
 
<math>T_{max}</math>, and if data permit, <math>T_{lag}</math>, <math>CL/F</math>, <math>V_z/F</math>, and <math>t_{1/2}</math>
 

### 2.3. Study Design

This is a single dose, open-label randomized, 4-period, 6-sequence crossover study in a single cohort of approximately 12 healthy male and/or female participants randomized to one of the sequences (containing 1 solution and 2 MR [MR1 and MR2] capsule formulations of ritlecitinib) displayed in Table 2. The first 3 periods are under fasted condition and the fourth period is under fed condition to investigate food effect on the PK of modified release formulations MR1 and MR2.

**Table 2. Study Design and Treatments**

Sequence	Period 1	Period 2	Period 3	Period 4
1 (n=2)	A	B	C	B, fed
2 (n=2)	B	C	A	B, fed
3 (n=2)	C	A	B	B, fed
4 (n=2)	A	B	C	C, fed
5 (n=2)	B	C	A	C, fed
6 (n=2)	C	A	B	C, fed

A: ritlecitinib 100 mg PO solution

B: ritlecitinib 100 mg (2 x 50 mg) MR1 capsules

C: ritlecitinib 100 mg (2 x 50 mg) MR2 capsules

### 3. ENDPOINTS AND BASELINE VARIABLES: DEFINITIONS AND CONVENTIONS

#### 3.1. Primary Endpoint(s)

The PK profile and relative bioavailability of ritlecitinib as 2 MR capsule formulations, MR1 and MR2, relative to solution formulation under fasted conditions will be derived from the concentration-time profiles as shown in the table below, if data permit.

Parameter	Definition	Method of Determination
$C_{\max}$	Maximum plasma concentration	Observe directly from the data
$AUC_{\text{last}}$	Area under the plasma concentration versus time curve from time zero to the time of last quantifiable concentration ( $C_{\text{last}}$ )	Linear/Log trapezoidal method
$AUC_{\text{inf}}^a$	Area under the plasma concentration versus time curve	$AUC_{\text{last}} + (C_{\text{last}}/k_{\text{el}})$ , where $C_{\text{last}}$ is the predicted plasma concentration at the last quantifiable time point estimated from the log-linear regression analysis; $k_{\text{el}}$ is the terminal phase rate constant calculated by a linear regression of the log-linear concentration-time curve

a If data permit.

#### 3.2. Secondary Endpoint(s)

To evaluate the effect of food on ritlecitinib exposure following administration as 2 MR formulations, MR1 and MR2, the following secondary endpoints for the PK of ritlecitinib will be derived from the concentration-time profiles as shown in the table below.

Parameter	Definition	Method of Determination
$C_{\max}$	Maximum plasma concentration	Observe directly from the data
$AUC_{\text{last}}$	Area under the plasma concentration versus time curve from time zero to the time of last quantifiable concentration ( $C_{\text{last}}$ )	Linear/Log trapezoidal method
$AUC_{\text{inf}}^a$	Area under the plasma concentration versus time curve	$AUC_{\text{last}} + (C_{\text{last}}/k_{\text{el}})$ , where $C_{\text{last}}$ is the predicted plasma concentration at the last quantifiable time point estimated from the log-linear regression analysis; $k_{\text{el}}$ is the terminal phase rate constant calculated by a linear regression of the log-linear concentration-time curve

a If data permit.

Another secondary endpoint is evaluating the safety and tolerability of ritlecitinib following single oral administration as MR1 and MR2 capsule formulations through the assessment of AEs, clinical laboratory tests, vital signs, and 12-lead electrocardiogram (ECG).

### 3.3. Tertiary/Exploratory Endpoint(s)

To estimate additional PK parameters of ritlecitinib following single oral administration as MR1 and MR2 capsule formulations in healthy adult participants, the following tertiary/exploratory endpoints for the PK of ritlecitinib will be derived from the concentration-time profiles as shown in the table below.

Parameter	Definition	Method of Determination
T max	Time for C max	Observed directly from data as time of first occurrence
t 1/2 a	Terminal half-life	Log e (2)/k el , where k el is the terminal phase rate constant calculated by a linear regression of the log-linear concentration-time curve. Only those data points judged to describe the terminal log-linear decline will be used in the regression
CL/F a	Apparent Clearance	Dose/AUC inf
Vz/F a	Apparent volume of distribution after oral dose	Dose/(AUC inf *k el ) after oral dose
T lag a	Lag time	Time prior to the time corresponding to the first quantifiable concentration

a if data permits.

### 3.4. Baseline Variables

**Start and end dates of study treatment:** The date of first dose (start date) of study treatment is the earliest date of non-zero dosing of the study drug. The date of last dose of study treatment is the latest date of non-zero dosing of the study drug.

**Definition of baseline:** For vital signs and ECG, the baseline measurement of Periods 1-3 is the last pre-dose measurement taken on Day 1 of Period 1, and the baseline measurement of Period 4 is the last pre-dose measurement taken on Day 1 of Period 4. For safety labs, the baseline measurement is the pre-dose measurement on Day -1.

### 3.5. Safety Endpoints

The following data are considered in standard safety summaries (see protocol for collection days, baseline assessment, and list of parameters):

- *adverse events*;
- *laboratory data*;
- *vital signs data*;
- *ECG results*.

### **3.5.1. Adverse Events**

An adverse event (AE) is considered a Treatment-Emergent Adverse Event (TEAE) if the event started during the effective duration of treatment. All events that start on or after the first dosing day and time/start time, if collected, but before the end of the last follow-up date, will be flagged as TEAEs. The algorithm will not consider any events that started prior to the first dose date. If an AE starts on the same day as the first dose date, it will be considered treatment emergent unless the CRF data indicates otherwise via explicitly recording time for AE onset which was occurred before the first treatment dosing.

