8.4.1. Time Period and Frequency for Collecting AE and SAE Information

The time period for actively eliciting and collecting AEs and SAEs ("active collection period") for each participant begins from the time the participant provides informed consent, which is obtained before undergoing any study-related procedure and/or receiving study intervention), through and including a minimum of 28 calendar days, except as indicated below, after the last administration of the study intervention.

Follow-up by the investigator continues throughout the active collection period and until the AE or SAE or its sequelae resolve or stabilize at a level acceptable to the investigator.

When a clinically important AE remains ongoing at the end of the active collection period, follow-up by the investigator continues until the AE or SAE or its sequelae resolve or stabilize at a level acceptable to the investigator and Pfizer concurs with that assessment.

For participants who are screen failures, the active collection period ends when screen failure status is determined.

If the participant withdraws from the study and also withdraws consent for the collection of future information, the active collection period ends when consent is withdrawn.

If a participant permanently discontinues or temporarily discontinues study intervention because of an AE or SAE, the AE or SAE must be recorded on the CRF and the SAE reported using the CT SAE Report Form.

Investigators are not obligated to actively seek information on AEs or SAEs after the participant has concluded study participation. However, if the investigator learns of any SAE, including a death, at any time after a participant has concluded study participation, and they consider the event to be reasonably related to the study intervention, the investigator must promptly report the SAE to Pfizer using the CT SAE Report Form.

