10.3.1. Definition of AE

AE Definition

- An AE is any untoward medical occurrence in a patient or clinical study participant, temporally associated with the use of study intervention, whether or not considered related to the study intervention.
- Note: An AE can therefore be any unfavorable and unintended sign (including an abnormal laboratory finding), symptom, or disease (new or exacerbated) temporally associated with the use of study intervention.

Events Meeting the AE Definition

- Any abnormal laboratory test results (hematology, clinical chemistry, or urinalysis) or other safety assessments (eg, ECG, radiological scans, vital sign measurements), including those that worsen from baseline, considered clinically significant in the medical and scientific judgment of the investigator. Any abnormal test results that meet any of the conditions below must be recorded as an AE:
 - Is associated with accompanying symptoms;
 - Requires additional diagnostic testing or medical/surgical intervention;
 - Leads to a change in study dosing (outside of any protocol-specified dose adjustments) or discontinuation from the study, significant additional concomitant drug treatment, or other therapy.
- Exacerbation of a chronic or intermittent preexisting condition, including an increase in either frequency and/or intensity of the condition.
- New condition detected or diagnosed after study intervention administration, even though it may have been present before the start of the study.
- Signs, symptoms, or the clinical sequelae of a suspected drug-drug interaction.
- Signs, symptoms, or the clinical sequelae of a suspected overdose of either study intervention or a concomitant medication. Overdose per se will not be reported as an AE or SAE unless it is an intentional overdose taken with possible suicidal/self-harming intent. Such overdoses should be reported regardless of sequelae.

Events NOT Meeting the AE Definition

- Any clinically significant abnormal laboratory findings or other abnormal safety assessments that are associated with the underlying disease, unless judged by the investigator to be more severe than expected for the participant's condition.
- The disease/disorder being studied or expected progression, signs, or symptoms of the disease/disorder being studied, unless more severe than expected for the participant's condition.
- Medical or surgical procedure (eg, endoscopy, appendectomy): the condition that leads to the procedure is the AE.

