- Situations in which an untoward medical occurrence did not occur (social and/or convenience admission to a hospital).
- Anticipated day-to-day fluctuations of preexisting disease(s) or condition(s) present or detected at the start of the study that do not worsen.

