- For each AE or SAE, the investigator must document in the medical notes that they have reviewed the AE or SAE and have provided an assessment of causality.
- There may be situations in which an SAE has occurred, and the investigator has minimal information to include in the initial report to the sponsor. However, it is very important that the investigator always make an assessment of causality for every event before the initial transmission of the SAE data to the sponsor.
- The investigator may change their opinion of causality in light of follow-up information and send an SAE follow-up report with the updated causality assessment.
- The causality assessment is one of the criteria used when determining regulatory reporting requirements.
- If the investigator does not know whether or not the study intervention caused the event, then the event will be handled as "related to study intervention" for reporting purposes, as defined by the sponsor. In addition, if the investigator determines that an SAE is associated with study procedures, the investigator must record this causal relationship in the source documents and CRF, and report such an assessment in the dedicated section of the CT SAE Report Form and in accordance with the SAE reporting requirements.

Follow-Up of AEs and SAEs

- The investigator is obligated to perform or arrange for the conduct of supplemental measurements and/or evaluations, as medically indicated or as requested by the sponsor, to elucidate the nature and/or causality of the AE or SAE as fully as possible. This may include additional laboratory tests or investigations, histopathological examinations, or consultation with other healthcare providers.
- If a participant dies during participation in the study or during a recognized follow-up period, the investigator will provide Pfizer Safety with a copy of any postmortem findings, including histopathology.
- New or updated information will be recorded in the originally submitted documents.
- The investigator will submit any updated SAE data to the sponsor within 24 hours of receipt of the information.

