Similarly to the analysis in [Section 6.1](#), the residuals from the model will be examined for normality and the presence of outliers via visual inspection of plots of residuals vs predicted values and normal probability plots of residuals but these will not be included in the clinical study report. If there are major deviations from normality or outliers then the effect of these on the conclusions will be investigated through alternative transformations and/or analyses excluding outliers. Justification for any alternative to the planned analysis will be given in the report of the study.

A listing of the descriptive and graphical summaries for PK parameters is presented in [Section 6.4](#).

In addition, for the parameters  $AUC_{inf}$  (if data permit),  $AUC_{last}$  and  $C_{max}$ , a listing of the individual subject ratios (Test/Reference) will also be provided. Box and whisker plots for individual subject parameters ( $AUC_{inf}$ ,  $AUC_{last}$  and  $C_{max}$ ) will be presented by treatment and overlaid with geometric means.

- *Assessment of AEs, clinical laboratory tests, vital signs and 12-lead ECG*

For the secondary endpoint concerning safety, adverse events, laboratory data, vital signs, ECG data, and other safety data will be listed and summarized in accordance with the sponsor reporting standards as described in [Section 3.5](#).

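### SAP 3.5.1 has no worsening clause, so an AE that begins before the first dose and worsens afterwards is flagged as treatment-emergent only if the worsening is recorded as a new event

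*SAP*

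**What the plan says.** The rule is in SAP 3.5.1: "An adverse event (AE) is considered a Treatment-Emergent Adverse Event (TEAE) if the event started during the effective duration of treatment". Events starting from the first dose up to the last follow-up date are flagged. For earlier events the SAP says: "The algorithm will not consider any events that started prior to the first dose date". An event on the day of the first dose is flagged unless a recorded onset time places it before dosing. Nothing is said about an event that was present before dosing and gets worse.

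The protocol provides the rest of the picture:

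- **Collection.** Under Protocol 8.4.1 the active collection period "begins from the time the participant provides informed consent". Screening may take place up to 28 days before the first dose.
- **Definition.** Protocol 10.3.1 counts as an AE: "Exacerbation of a chronic or intermittent preexisting condition, including an increase in either frequency and/or intensity of the condition". It excludes: "Anticipated day-to-day fluctuations of preexisting disease(s) or condition(s) present or detected at the start of the study that do not worsen".
- **Recording.** Protocol 10.3.3, on follow-up of AEs, says: "New or updated information will be recorded in the originally submitted documents". Protocol 10.1.7 leaves CRF entry rules to a separate completion document.
- **Endpoint and output.** The secondary safety endpoint in SAP 2.2 is "Assessment of AEs, clinical laboratory tests, vital signs and 12-lead ECG". SAP 6.2 says that these data "will be listed and summarized in accordance with the sponsor reporting standards".

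**The concern.** Treatment emergence should pick out what appears or gets worse after exposure. The SAP's flag covers only what appears. An AE that began in screening or on Day -1, was mild at the first dose and became moderate, severe or serious after ritlecitinib keeps a pre-dose start date if it stays on one record. The algorithm then never flags it.

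Safety and tolerability of MR1 and MR2 is a secondary objective. Protocol 8.4.8 names gastrointestinal events of special interest, among them constipation, diarrhea, nausea and abdominal pain, to assess local tolerability. Complaints of this kind can be present at a low level before dosing, and their worsening after a modified-release capsule is part of what the study should detect. Leaving out a worsening clause can only lower the TEAE count.

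**Working it through.** The point concerns a definition, so the plan has no figure of its own to reproduce. The check applies the rule to the possible ways of recording an event and then shows the scale.

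**Step 1: the rule.** From SAP 3.5.1, an event is flagged if its start is at or after the first dose and before the end of follow-up. Intensity and seriousness are not inputs.

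**Step 2: three cases.**

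| Case | Start date used | TEAE flag |
|---|---|---|
| 1. Onset after consent and before the first dose; worsens after dosing; kept on one record | Before dosing | No |
| 2. Same course, with the worsening entered as a new AE | After dosing | Yes |
| 3. Onset on the first dose date, recorded time before dosing | Before dosing | No |

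Cases 1 and 2 describe the same clinical course and are classified differently. Case 3 behaves like case 1 if the event later worsens.

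**Step 3: which case applies?** Protocol 10.3.1 makes an exacerbation of a preexisting condition an AE, which favors case 2. Protocol 10.3.3 puts updated information into the documents already submitted, which makes case 1 plausible. Neither passage says whether a rise in intensity opens a new entry with its own onset date. The supplied documents do not settle the question.

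**Step 4: scale.** Inputs: 12 participants, 2 in each of 6 sequences (Protocol 9.5).

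- One affected participant: 1/12 = 8.3 percentage points.
- The documents give no rate of AEs ongoing at the first dose that later worsen. Let p be an assumed probability per participant. The chance of at least one such participant is 1 − (1 − p)^12, and the expected number is 12p:

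| Assumed p | At least 1 of 12 | Expected number |
|---|---|---|
| 1% | 11.4% | 0.12 |
| 2% | 21.5% | 0.24 |
| 5% | 46.0% | 0.60 |
| 10% | 71.8% | 1.20 |

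These are upper limits on misclassification at each p, because any worsening recorded as a new AE is flagged correctly. No sample size or confidence interval width in the plan depends on the rule.

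**The case against.** The case against giving this weight is substantial, and much of it stands.

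- **The event is not lost.** A reader might infer that it is left out of the safety endpoint. The documents do not support that. The endpoint is assessment of AEs, the list in SAP 3.5 names adverse events and not TEAEs, and SAP 6.2 lists and summarizes them. No table in SAP Section 6 is visibly restricted to TEAEs. Whether the summaries use the flag depends on sponsor standards that are not supplied.
- **The protocol's AE definition may already solve the problem.** A reader might infer that the SAP contradicts Protocol 10.3.1. It does not, strictly. If an exacerbation is an AE in its own right and is entered with its own onset, the algorithm flags it. The gap is that nothing in the supplied documents requires that entry.
- **Recording rules may exist elsewhere.** The CRF completion document named in Protocol 10.1.7 may already call for a new line when intensity changes. This cannot be checked.
- **Serious worsening has its own route.** SAEs in the collection period are reported to the sponsor within 24 hours and recorded on the CRF, whatever the TEAE flag.
- **Rates are probably low.** Participants are healthy, clinically significant gastrointestinal disease is excluded, and eligibility is checked again on Day -1. Only AEs still ongoing at the first dose matter, so the 28-day screening window does not measure the risk.
- **The algorithm is generous elsewhere.** It flags any onset up to the last follow-up date, and first-dose-day events with no recorded time. The missing clause lowers the count, but the algorithm as a whole is not shown to undercount.

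These points limit the consequence. They do not supply the missing clause or override the explicit exclusion of events that started before the first dose.

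**Conclusion.** The point holds in a limited form. The SAP's TEAE rule has no provision for worsening, so an AE with onset between consent and the first dose that worsens or becomes serious after dosing loses the flag when it stays on its original record. It keeps its place as a recorded and listed AE. Classification therefore depends on recording practice that neither document fixes.

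The expected impact is small: 12 healthy participants, single doses, descriptive safety summaries and no hypothesis test. One affected participant would move a proportion of 12 by 8.3 percentage points. How likely that is rests entirely on an assumed rate.

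A reader might quote 1/6 = 16.7 points for a fed group of 6. That is a poor guide. The exclusion applies only to onset before the Period 1 dose, so such an event would have to persist to Period 4, Study Day 10 in the Schedule of Activities, and worsen then.

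This is a cheap improvement, not a threat to the study's conclusions.

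**What to change.** Add one sentence to SAP 3.5.1: an AE present before the first dose that increases in intensity or becomes serious on or after the first dose is treatment-emergent, counted from the date of worsening.

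Then confirm that the CRF completion instructions capture that date, for example by requiring a new AE line when an AE already recorded before dosing worsens. If they already do so, a cross-reference in the SAP is enough.

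The cost is one SAP sentence and, at most, one CRF instruction. The TEAE count may be slightly higher. Nothing else in the plan changes.
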